#### Exclusion Criteria:

1. Hypersensitivity or allergy to acamprosate
2. Current use of wellbutrin and not willing to switch to an acceptable antidepressant medication
3. Renal impairment (creatinine level >1.5 mg/dL);
4. Diagnosis of advanced liver disease indicated in the medical record or by a MELD score of above 10;
5. Women who are pregnant, breastfeeding, or planning to become pregnant during the next year;
6. Primary diagnosis of substance use disorder other than alcohol as determined by PRISM or in medical record review or secondary diagnosis of active (within the past year) benzo/sedative dependence, opioid dependence, stimulant dependence, heroin dependence, and/or cocaine dependence
7. Refusal to abstain from any chronic/daily use of prescribed benzodiazepines, opioids, stimulants, cannabis related medication such as CBD or medical marijuana, during the course of participation.
8. Current use of Naltrexone and not willing to stop and switch to Acamprosate/Placebo\* (see notation dated 5-12-2023 above)
9. Current use of Antabuse.

10. Active suicidal ideation or any unstable medical or psychiatric condition as determined by responses to PRISM or by the investigator.
11. Status of involuntary or court-ordered admission at time of consent.

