### ***Study Assessments and Procedures***

#### **Assessments**

A standardized clinical assessment is performed for all patients admitted to above mentioned treatment programs. This assessment will be used by study personnel to determine study eligibility, and determine if there is a need to discuss treatment of depression and/or anxiety. The Study Psychiatrist affiliated with each study site, or a member of the clinical treating team will meet with the patient to assess appropriateness and discuss potential benefits and risks associated. For patients meeting study inclusion and exclusion criteria and signing Informed Consent, the presence of AUD and comorbid conditions including depressive and anxiety disorders will be confirmed by Psychiatric Research Interview for Substance and Mental disorders (PRISM). The severity of depression and anxiety symptoms will be assessed by the Patient Health Questionnaire (PHQ-9) and Generalized Anxiety Disorder (GAD-7), respectively. In addition, alcohol use history, alcohol craving intensity, LFT levels and other relevant measures will be assessed at baseline and repeated at follow up visits as defined in Table 1.

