**Table 1: Study Assessments**

Study Assessments	Baseline Evaluation	Follow-Up Visits					
		2 week – TC	1 month #	6 week – TC	2 month #	10 week – TC	3 month #
Blood Collection	X		X				X
Medication provided	X		X		X		
PRISM	X						
LTDH	X						
CIWA-Ar	X						
TLFB ♦ (BDQ)	X		X		X		X
PHQ-9	X	X	X	X	X	X	X
GAD7	X	X	X	X	X	X	X
AAM			X		X		X
IDTS	X						
PACS	X		X				X
PRISE	X		X		X		X
FIBSER			X		X		X
PSQI	X		X		X		X
FIRM	X						
CD-RISC	X						X
Med. Compliance			X		X		X
Med. Compliance Enhancement		X		X		X	
CTA	X						
GGT lab test	X		X				X
CTQ	X						
CGI			X**		X**		

**Definitions:** AAM: AA attendance monitoring. CIWA-R: Clinical Institute Withdrawal Assessment-Research. CTA: Commitment to Abstinence. CTQ: Childhood Trauma Questionnaire. FIBSER: Frequency, Intensity and Burden of Side Effects Ratings. GGT: gamma-glutamyl transpeptidase lab test. IDTS: Inventory of Drug Taking Situations. LTDH: Lifetime Drinking History. PACS: Penn Alcohol Craving Scale. PHQ-9: Patient Health Questionnaire 9-item. GAD7: Generalized Anxiety Disorder 7-item. PRISE: Patient-rated Inventory of Side Effects. PRISM: Psychiatric Research Interview for Substance and Mental Disorders. TC: Telephone Call TLFB: The Alcohol Timeline Follow Back. PSQI: Pittsburgh Sleep Quality Index. FIRM: Family Index of Risk for Mood. CD-RISC: Connor-Davidson Resilience Scale (CD-RISC); CGI: Clinical Global Impression (CGI); \*\*Used by study psychiatrist to assess worsening mood symptoms despite antidepressant treatment during study participation. ♦ Brief Drinking Questionnaire (BDQ). # Allow the use of alternative formats to face-to-face visits based on concern for COVID exposure or other circumstances potentially preventing patients from attending face-to-face visits (blood draw done in person).

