### Subject Information

Target accrual: 800 (400 Mayo Clinic; 400 Hazelden Addiction Treatment Centers)

Subject population: Adults (male and female)

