### Research Activity

Check all that apply and complete the appropriate sections as instructed.

1.  **Drug & Device:** Drugs for which an investigational new drug application is not required. Device for which (i) an investigational device exemption application is not required; or the medical device is cleared/approved for marketing and being used in accordance with its cleared/approved labeling. (Specify in the Methods section)
2.  **Blood:** Collection of blood samples by finger stick, heel stick, ear stick, or venipuncture.
3.  **Biological specimens other than blood:** Prospective collection of human biological specimens by noninvasive means that may include: urine, sweat, saliva, buccal scraping, oral/anal/vaginal swab, sputum, hair and nail clippings, etc.
4.  **Tests & Procedures:** Collection of data through noninvasive tests and procedures routinely employed in clinical practice that may include: MRI, surface EEG, echo, ultrasound, moderate exercise, muscular strength & flexibility testing, biometrics, cognition testing, eye exam, etc. (Specify in the Methods section)
5.  **Data** (medical record, images, or specimens): Research involving use of existing and/or prospectively collected data.
6.  **Digital Record:** Collection of electronic data from voice, video, digital, or image recording. (Specify in the Methods section)
7.  **Survey, Interview, Focus Group:** Research on individual or group characteristics or behavior, survey, interview, oral history, focus group, program evaluation, etc. (Specify in the Methods section)

NIH has issued a *Certificate of Confidentiality* (COC). *When checked, provide the institution and investigator named on the COC and explain why one was requested.* \_\_\_\_\_

## Biospecimens – Categories 2 and 3

(2) Collection of blood samples. When multiple groups are involved copy and paste the appropriate section below for example repeat section b when drawing blood from children and adults with cancer.

a. **From healthy, non-pregnant, adult subjects who weigh at least 110 pounds.** For a minimal risk application, the amount of blood drawn from these subjects may not exceed 550ml in an 8 week period and collection may not occur more frequently than 2 times per week.

Hazelden Betty Ford Treatment facilities in Plymouth, MN and Newburg, OR, Mayo Clinic Health System site in Albert Lea, MN patient blood volume per blood draw: 35ml

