Other location's (Mayo Clinic Rochester & Hazelden Betty Ford, Center City, MN) patients' blood volume per blood draw: 50ml at Baseline (preferred but can be done at any visit) and 35 ml at Months 1 & 3

Hazelden Center City will offer participants to provide the additional ~15ml of blood as optional (preferred at baseline visit but can be done at any visit) for generation of the induced pluripotent stem cells (iPSCs) from peripheral blood mononuclear cells (PBMC) as described below.

Frequency of blood draw: three time points, Baseline, 1 and 3 month visits.

Blood samples for 35ml collection are for GGT levels: Serum Separator Tube (SST); DNA extraction, Acamprosate blood levels, Metabolomic, Proteomic biomarkers (EDTA tubes), and mRNA (PAXGene tube). The process of spinning and aliquoting the samples will be completed at each site. EDTA tubes that would need to be kept on ice, centrifuged in the cold (NOT frozen) with the plasma aliquoted into 200 ul aliquots which would need to be immediately placed and stored at minus 80 degrees. The current metabolomic platform would include both the amines and neuromodulators. Acamprosate blood drug levels will be plasma aliquoted into 300 ul aliquots and also assayed with these samples. PAXGene tube is placed directly into the minus 80 degree freezer.

An additional 15 ml of blood collected in EDTA tubes for peripheral blood mononuclear cells (PBMC) isolation. The separation and banking of PBMCs will be performed in the laboratory, frozen and stored in liquid nitrogen. PBMC are used to generate induced pluripotent stem cells (iPSCs), a cell type that can self-renew and which can be differentiated into many cell types from many human tissues.

## Review of medical records, images, specimens – Category 5

**For review of existing data:** provide a date range or an end date for when the data was generated. The end date can be the date this application was submitted to the IRB. Example: 01/01/1999 to 12/31/2015 or all records through mm/dd/yyyy.

**Date Range:** 12/29/2004 to 07/09/2013

Check all that apply (data includes medical records, images, specimens).

(5a) Only data that exists before the IRB submission date will be collected.

(5b) The study involves data that exist at the time of IRB submission **and** data that will be generated after IRB submission. Include this activity in the Methods section.

(5c) The study will use data that have been collected under another IRB protocol.

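### Pregnancy is an exclusion, but no scheduled step rechecks it during the three months of treatment, although study drug is supplied again at months 1 and 2

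*Combined protocol and SAP*

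**What the plan says.** The Exclusion Criteria, item 5, rule out "Women who are pregnant, breastfeeding, or planning to become pregnant during the next year". The item names no source, method or date for the determination. Both sexes are enrolled from age 18 to 85 (Subject Information; Inclusion Criteria, item 1).

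Eligibility draws on a standardized clinical assessment made at admission to the treatment programme. The Assessments section says of it: "This assessment will be used by study personnel to determine study eligibility". Its contents are not listed. A study psychiatrist or a member of the treating team then meets the patient to judge suitability.

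Treatment lasts three months. In Table 1 the row "Medication provided" is marked at baseline, month 1 and month 2. The blood schedule in the Biospecimens section reads "Frequency of blood draw: three time points, Baseline, 1 and 3 month visits", so the month-2 dispensing visit has no draw. The footnote to Table 1 allows the monthly visits to be held other than face to face, with blood still drawn in person.

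The only other mention of pregnancy is a printed category heading on blood volumes: "From healthy, non-pregnant, adult subjects who weigh at least 110 pounds". That heading is not a test or a follow-up step.

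**The concern.** By including women who plan a pregnancy in the next year, item 5 shows that the protocol's concern extends past the day of entry. It covers the whole treatment period, and nothing scheduled in that period carries it through. An admission assessment, however thorough, cannot detect a pregnancy that starts later.

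What is at stake is participant safety as the protocol itself defines it. A condition that would have barred the first supply of study drug could be present at the second or third without the team being prompted to ask. Since the notation of 5-12-2023 (Study Medications), newly enrolled participants all receive acamprosate, so for them each repeat supply is active drug.

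**Working it through.** The plan gives no figure to reproduce. The check is a reading of each place where a recheck could stand, followed by a simple scaling.

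**Where a recheck during treatment could appear**

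- Table 1: no pregnancy row at any visit. GGT is the only named laboratory test, at baseline, month 1 and month 3.
- Telephone calls at weeks 2, 6 and 10 (Table 1): PHQ-9, GAD-7 and medication-compliance enhancement only.
- Tube list (Biospecimens): "Blood samples for 35ml collection are for GGT levels: Serum Separator Tube (SST); DNA extraction", then acamprosate level, metabolomic and proteomic markers and mRNA, with an additional tube for stem-cell work. No pregnancy assay is listed.
- Potential Side Effects and In-study risks and safety procedures: side effects, mood, suicidality and referral. There is no pregnancy question, contraception requirement or pregnancy reporting step.

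Set against the dispensing row, this gives:

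| Supply of study drug | Blood drawn | Pregnancy check named in the plan |
|---|---|---|
| Baseline | yes | none named; the admission assessment may cover it |
| Month 1 | yes | none |
| Month 2 | no | none |

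Both repeat supplies can therefore take place, with the plan followed exactly, without anyone asking about pregnancy.

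**Why the same reading does not settle the entry question**

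Table 1 is not a complete list of screening tests. Creatinine is needed for exclusion 3, and bilirubin, creatinine and INR for the MELD score in exclusion 4. None of them has a row in Table 1 or a place in the tube list. A pregnancy test could be missing from Table 1 for the same reason.

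**Scale**

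The inputs are the male counts in Table 2 and the target accrual of 800. The assumption is that the new cohort has the sex mix of one of the earlier cohorts. Women = N − men; share = women / N; expected number = share × 800.

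- PREDICT: 426 − 328 = 98; 98/426 = 23.0%; 0.230 × 800 = 184
- COMBINE: 1393 − 955 = 438; 438/1393 = 31.4%; 0.3144 × 800 = about 252
- CITA: 443 − 286 = 157; 157/443 = 35.4%; 0.3544 × 800 = about 284

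The range is about 184 to 284 women. Because enrolment runs to age 85, this is an upper bound on those to whom the question applies. The documents do not give the share of child-bearing potential, and no count of pregnancies can be derived.

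**The case against.** The strongest reply has four parts.

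- **Entry.** A reader might infer that exclusion 5 is never verified. The documents do not support that. Eligibility rests on an admission assessment of unlisted content, and Table 1 omits required laboratory tests as well. Whether a woman plans a pregnancy can only be learned by asking, so some interview is implied. What stands at entry is a gap in documentation: the source and date of the determination are not stated.
- **Detection.** A reader might infer that a pregnancy on treatment would go unseen. That is also too strong. There is scheduled contact about every two weeks, adverse effects are assessed at follow-up visits, and a participant may mention a pregnancy at any of these. The supportable statement is that it can go undetected because nothing prompts the question.
- **Text not available.** The consent pages were not part of the text reviewed, and instructions on contraception or pregnancy reporting may be there. They would not by themselves put a check into the visit schedule.
- **Harm.** The documents give no reason for exclusion 5 and describe no fetal risk from acamprosate or the antidepressants. The point therefore rests on the protocol's own exclusion and claims no size of harm.

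A serum assay before first dispensing, with no extra visit, is also tempting. It cannot be recommended from these documents: blood collection and first dispensing share the baseline visit, and neither assay turnaround nor spare serum volume is given.

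After all four, the gap during treatment remains. It does not depend on what the admission assessment contains.

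**Conclusion.** The point holds for the treatment period. In the documents available, a safety exclusion that looks a year ahead has no scheduled follow-through over three months, and two of the three supplies of study drug are made without a prompt to ask. A pregnancy that begins on treatment can go undetected unless the participant reports it.

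At entry the point reduces to missing detail about which determination counts and how recent it must be. The date matters because inclusion criterion 2 allows up to 35 days since the last drink, so an admission finding, if there is one, could be some weeks old.

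The group concerned lies within about 184 to 284 women of 800, if the Table 2 sex mix carries over. The number of child-bearing potential is unknown. The conclusion also assumes that the consent pages contain no scheduled recheck. It is a modest, inexpensive safety improvement and has no bearing on the power or validity of the analyses.

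**What to change.** Two changes:

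1. Add a pregnancy-status question to Table 1 at the existing month-1 and month-2 dispensing visits. A question can be asked whether or not the visit is face to face, and it does not depend on a blood draw, which month 2 lacks.
2. Reconcile exclusion 5 with the Assessments section and Table 1 by naming the source of the entry determination and the date or window to which it refers.

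Whether a test is used, which one, and what follows a positive answer are for the investigators to define.

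The cost is one added form item and a little staff time at visits already planned. The second change is a clarification of text.

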### Research Activity

Check all that apply and complete the appropriate sections as instructed.

1.  **Drug & Device:** Drugs for which an investigational new drug application is not required. Device for which (i) an investigational device exemption application is not required; or the medical device is cleared/approved for marketing and being used in accordance with its cleared/approved labeling. (Specify in the Methods section)
2.  **Blood:** Collection of blood samples by finger stick, heel stick, ear stick, or venipuncture.
3.  **Biological specimens other than blood:** Prospective collection of human biological specimens by noninvasive means that may include: urine, sweat, saliva, buccal scraping, oral/anal/vaginal swab, sputum, hair and nail clippings, etc.
4.  **Tests & Procedures:** Collection of data through noninvasive tests and procedures routinely employed in clinical practice that may include: MRI, surface EEG, echo, ultrasound, moderate exercise, muscular strength & flexibility testing, biometrics, cognition testing, eye exam, etc. (Specify in the Methods section)
5.  **Data** (medical record, images, or specimens): Research involving use of existing and/or prospectively collected data.
6.  **Digital Record:** Collection of electronic data from voice, video, digital, or image recording. (Specify in the Methods section)
7.  **Survey, Interview, Focus Group:** Research on individual or group characteristics or behavior, survey, interview, oral history, focus group, program evaluation, etc. (Specify in the Methods section)

NIH has issued a *Certificate of Confidentiality* (COC). *When checked, provide the institution and investigator named on the COC and explain why one was requested.* \_\_\_\_\_

## Biospecimens – Categories 2 and 3

(2) Collection of blood samples. When multiple groups are involved copy and paste the appropriate section below for example repeat section b when drawing blood from children and adults with cancer.

a. **From healthy, non-pregnant, adult subjects who weigh at least 110 pounds.** For a minimal risk application, the amount of blood drawn from these subjects may not exceed 550ml in an 8 week period and collection may not occur more frequently than 2 times per week.

Hazelden Betty Ford Treatment facilities in Plymouth, MN and Newburg, OR, Mayo Clinic Health System site in Albert Lea, MN patient blood volume per blood draw: 35ml

Other location's (Mayo Clinic Rochester & Hazelden Betty Ford, Center City, MN) patients' blood volume per blood draw: 50ml at Baseline (preferred but can be done at any visit) and 35 ml at Months 1 & 3

Hazelden Center City will offer participants to provide the additional ~15ml of blood as optional (preferred at baseline visit but can be done at any visit) for generation of the induced pluripotent stem cells (iPSCs) from peripheral blood mononuclear cells (PBMC) as described below.

Frequency of blood draw: three time points, Baseline, 1 and 3 month visits.

Blood samples for 35ml collection are for GGT levels: Serum Separator Tube (SST); DNA extraction, Acamprosate blood levels, Metabolomic, Proteomic biomarkers (EDTA tubes), and mRNA (PAXGene tube). The process of spinning and aliquoting the samples will be completed at each site. EDTA tubes that would need to be kept on ice, centrifuged in the cold (NOT frozen) with the plasma aliquoted into 200 ul aliquots which would need to be immediately placed and stored at minus 80 degrees. The current metabolomic platform would include both the amines and neuromodulators. Acamprosate blood drug levels will be plasma aliquoted into 300 ul aliquots and also assayed with these samples. PAXGene tube is placed directly into the minus 80 degree freezer.

An additional 15 ml of blood collected in EDTA tubes for peripheral blood mononuclear cells (PBMC) isolation. The separation and banking of PBMCs will be performed in the laboratory, frozen and stored in liquid nitrogen. PBMC are used to generate induced pluripotent stem cells (iPSCs), a cell type that can self-renew and which can be differentiated into many cell types from many human tissues.

## Review of medical records, images, specimens – Category 5

**For review of existing data:** provide a date range or an end date for when the data was generated. The end date can be the date this application was submitted to the IRB. Example: 01/01/1999 to 12/31/2015 or all records through mm/dd/yyyy.

**Date Range:** 12/29/2004 to 07/09/2013

Check all that apply (data includes medical records, images, specimens).

(5a) Only data that exists before the IRB submission date will be collected.

(5b) The study involves data that exist at the time of IRB submission **and** data that will be generated after IRB submission. Include this activity in the Methods section.

(5c) The study will use data that have been collected under another IRB protocol.

Data  Specimens  Data & Specimens IRB #16-004978 “Pharmacogenomics of Treatment Outcomes in Alcohol Use Disorders”

Data  Specimens  Data & Specimens IRB #07-007204 “A Pharmacogenomic Probe Study of Acamprosate: Genes Associated with Response” Mayo Clinic Center for the Individualized Treatment of Alcohol Dependence” (CITA) Recruitment dates: 03/14/2008 to 02/01/2013

Data  Specimens  Data & Specimens IRB #2681-04 “Developing a DNA Repository for Genomic Studies of Addiction” (GOA) Recruitment dates: 12/29/2004 to 07/09/2013

(5d) This study will obtain data generated from other sources. Examples may include receiving data from participating sites or an external collaborator, accessing an external database or registry, etc. Explain the source and how the data will be used in the Methods section.

(6) Video audio recording: *Describe the plan to maintain subject privacy and data confidentiality, transcription, store or destroy, etc.*

### **HIPAA Identifiers and Protected Health Information (PHI)**

Protected health information is medical data that can be linked to the subject directly or through a combination of indirect identifiers.

Recording identifiers (including a code) during the conduct of the study allows you to return to the medical record or data source to delete duplicate subjects, check a missing or questionable entry, add new data points, etc. De-identified data is medical information that has been stripped of all HIPAA identifiers so that it cannot be linked back to the subject. De-identified data is **rarely** used in the conduct of a research study involving a chart review.

**Review the list of subject identifiers below and, if applicable, check the box next to each HIPAA identifier being recorded at the time of data collection or abstraction.** Identifiers apply to any subject enrolled in the study including Mayo Clinic staff, patients and their relatives and household members.

**Internal** refers to the subject's identifier that will be recorded at Mayo Clinic by the study staff.

**External** refers to the subject's identifier that will be shared outside of Mayo Clinic.

Check all that apply:	INTERNAL	EXTERNAL
Name	X	
Mayo Clinic medical record or patient registration number, lab accession, specimen or radiologic image number	X	
Subject ID, subject code or any other person-specific unique identifying number, characteristic or code that can link the subject to their medical data	X	
Dates: All elements of dates [month, day, and year] directly related to an individual, their birth date, date of death, date of diagnosis, etc.	X	
Note: Recording a year only is not a unique identifier.		
Social Security number		
Medical device identifiers and serial numbers		
Biometric identifiers, including finger and voice prints, full face photographic images and any comparable images		
Web Universal Resource Locators (URLs), Internet Protocol (IP) address numbers, email address		
Street address, city, county, precinct, zip code, and their equivalent geocodes		
Phone or fax numbers		
Account, member, certificate or professional license numbers, health beneficiary numbers		
Vehicle identifiers and serial numbers, including license plate numbers		
Check 'None' when none of the identifiers listed above will be recorded, maintained, or shared during the conduct of this study. (exempt category 4)	 None	 None

